8.2.1 Partial or Missing Dates

The following conventions will be used to impute missing portions of dates for AEs and concomitant medications. Note that the imputed values outlined here may not always provide the most conservative date. In those circumstances, the imputed value may be replaced by a date that will lead to a more conservative analysis.

Start Dates:

- 1. If the year is unknown, then the date will not be imputed and will be assigned a missing value.
- 2. If the month is unknown, then:
 - a. The month and day of the first dose date will be imputed if the year matches the first dose date year.
 - b. Otherwise, 'January' will be assigned.
- 3. If the day is unknown, then:
 - a. The day of the first dose date will be imputed if the month and year match the first dose date month and year.
 - b. Otherwise, the first day of the month will be assigned.

Stop Dates:

- 1. If the year is unknown, then the date will not be imputed and will be assigned a missing value.
- 2. If the month is unknown, then 'December' will be assigned.
- 3. If the day is unknown, then the last day of the month will be assigned.

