### 2.3 Safety Objectives

The overall safety objective is to assess severity, incidence and frequency of AEs, AEs of Special Interest (AESIs), and Serious Adverse Events (SAEs), concomitant medication use, suicidal ideation and behavior, and vital signs to support the package insert for MDMA-assisted psychotherapy. The following safety objectives will evaluate the safety of MDMA-assisted psychotherapy.

1. Assess incidence of AEs during Experimental Sessions that may be indicative of a medical complication of the Investigational Product (IP), such as clinical signs and

- symptoms of chest pain, shortness of breath, or neurological symptoms or any other signs or symptoms that prompt additional vital sign measurements.
- 2. Assess incidence of AEs by severity.
- 3. Assess incidence of Treatment Emergent AEs (TEAEs) by severity.
- 4. Assess incidence of TEAEs by severity taken during an Experimental Session and through 2 days after IP administration.
- 5. Assess incidence of AESIs, defined as AEs specified in the protocol related to cardiac function and abuse liability.
- 6. Assess incidence of AEs by severity categorized as leading to discontinuation of IP, resulting in death or hospitalization, and continuing at Study Termination.
- 7. Assess incidence of SAEs.
- 8. Assess incidence of psychiatric concomitant medications taken during an Experimental Session and through 2 days after IP administration.
- 9. Assess incidence of any psychiatric concomitant medications taken during the Treatment Period.
- 10. Assess incidence of serious suicidal ideation and positive suicidal behavior assessed with the Columbia Suicide Severity Rating Scale (C-SSRS).
- 11. Assess mean changes in blood pressure, heart rate, and body temperature from pre-IP administration to end of each Experimental Session.

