## 13.1.2 Safety Analyses

Safety data will be summarized by exposure to IP, unsolicited AEs, concomitant medications, suicidal ideation and behavior, and vital signs overall. If a participant has more than one AE mapped to the same PT, that AE will be reported once using the highest severity. AEs that occur on Day 0 (Experimental Session), Day 1, Day 2 after IP administration will be presented separately. Report incidence of AEs during Experimental Sessions such as clinical signs and symptoms, such as chest pain, shortness of breath, or neurological symptoms or any other signs or symptoms that may be indicative of a medical complication of the IP.

Frequency and incidence of concomitant medications will be displayed by generic name, sorted by class, and summarized by analysis set and category. Concomitant medications taken on Day 0 (Experimental Session), Day 1, Day 2 after IP administration will be presented separately. Any psychiatric concomitant medications will be tabulated by period (Preparatory, Treatment Period, Follow-up Period). Frequency and incidence of positive or serious ideation and suicidal behavior will be presented using descriptive statistics of C-SSRS scores in tabular format. Vital signs (heart rate, blood pressure, and body temperature) for Experimental Sessions will be summarized using descriptive statistics in tabular format listing values at pre-IP administration, prior to the supplemental dose, and at the end of each Experimental Session. Additional details are available in the Statistical Analysis Plan.

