8.8.3 Concomitant Medications

A secondary measure of safety will be the reporting of concomitant medications. All concomitant medications collected from Screening to Study Termination will be categorized as follows:

- Pretreatment medications are defined as medications taken prior to and after signing informed consent and those taken during the Preparatory Period prior to the first Experimental Session. A stop date is expected prior to the first Experimental Session for any medications requiring a change in dose, a skipped dose, or tapering.
- Treatment Period concomitant medications are defined as those taken or continued during the Treatment Period from the first Experimental Session to the last Integrative Session. A stop date is expected prior to the each Experimental Session for any medications requiring a change in dose, a skipped dose, or tapering.
- Concomitant medications with a start date of the day of and two days after IP administration

- Follow-up Period concomitant medications are defined as those taken or continued during the Follow-up Period after the last Integrative Session through Termination
- Any concomitant medications that are tapered
- Any concomitant medications that are taken to treat an AE
- Any concomitant medications that are taken to treat an SAE
- Any excluded concomitant medications taken as a deviation from the protocol.

Concomitant medications on case report forms will be classified using the WHO Drug Dictionary EnhancedTM (WHO DDE). Frequency and incidence of concomitant medications will be displayed by generic name, sorted by class, and summarized by treatment group, analysis set, and category as defined above. Concomitant medications will be analyzed and presented as follows:

- Concomitant medications taken on the day of and two days after IP administration will be presented separately
- Any psychiatric concomitant medications by period.

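### SAP 8.2.1 can misplace partly dated adverse events and drugs around the dosing days, and SAP 8.8.3 gives two conflicting definitions for safety objective 8

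*SAP*

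**What the plan says.** SAP 8.2.1 applies one set of rules to partly dated adverse events (AEs) and concomitant medications.

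- Start, month unknown: "The month and day of the first dose date will be imputed if the year matches the first dose date year".
- Start, day unknown: "The day of the first dose date will be imputed if the month and year match the first dose date month and year". In any other month, "Otherwise, the first day of the month will be assigned".
- Stop: "If the month is unknown, then 'December' will be assigned", and "If the day is unknown, then the last day of the month will be assigned".

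If the year is unknown, nothing is imputed. An introductory note allows an imputed date to be swapped for a more conservative one. The swap is optional and the SAP does not define the term.

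On drugs around dosing, protocol 2.3, safety objective 8, reads "Assess incidence of psychiatric concomitant medications taken during an Experimental Session and through 2 days after IP administration". Protocol 13.1.2 reads "Concomitant medications taken on Day 0 (Experimental Session), Day 1, Day 2 after IP administration will be presented separately". The category list in SAP 8.8.3 instead has "Concomitant medications with a start date of the day of and two days after IP administration". A bullet at the end of the same SAP section returns to drugs taken on those days.

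**The concern.** Three features of these rules can put records in the wrong place.

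1. **Tapered drugs.** An imputed start is not checked against a known stop, and an imputed stop is not capped at dosing. Protocol 11.1 requires washout before Session 1, so a drug already cleared could be tabulated as present on the dosing day.
2. **Session 2.** Dosing happens twice, but the start rules know only the first dose. A partly dated AE from Session 2 has no rule that can bring it back to Session 2.
3. **Started or taken.** A category built on start dates leaves out a drug begun earlier and still in use at a session, even when every date is complete.

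The day 0-2 tables answer safety objectives 4 and 8, and protocol 2.3 says the safety data are to support the package insert. With at most 40 participants, one misplaced participant moves an incidence by at least 1/40 = 2.5 percentage points.

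**Working it through.** The plan states no figure on this point, so there is none to reproduce.

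**Inputs.** Session 2 is 21 to 35 days after Session 1 (protocol 4.1, Table 1). Tapered drugs stop at least five half-lives plus one week before Session 1 (protocol 11.1), so last intake is more than 7 days before. Each window is the session day and the two days after (SAP 8.8.2 and 8.8.3).

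**Assumptions not in the documents.** Session 1 is equally likely on any day of a 365-day year, all gaps are equally likely, and an AE is placed by its imputed start date.

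**Step 1: an illustration.** Session 1 on 21 March 2022, Session 2 on 18 April 2022.

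| Record | Known part | True date | Imputed date | Result |
|---|---|---|---|---|
| Drug start | year | January 2022 | 21 March | on the dosing day, after its true stop on 7 March |
| Drug stop | month, year | 7 March | 31 March | spans the Session 1 day |
| Drug stop | year | 7 March | December | spans the Session 1 day |
| AE start | month, year | 18 April | 1 April | outside both windows |
| AE start | year | 18 April | 21 March | counted at Session 1 |

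**Step 2: tapered drugs.** With the stop day missing, the imputed stop is on or after Session 1 whenever the true stop lies in the same calendar month. For last intake k days before Session 1 and a month of L days, that is L − k days (zero if k ≥ L). The year has seven months of 31 days, four of 30 and one of 28.

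- k = 8: 7×23 + 4×22 + 20 = 269; 269/365 = 74%
- k = 14: 7×17 + 4×16 + 14 = 197; 197/365 = 54%
- k = 21: 7×10 + 4×9 + 7 = 113; 113/365 = 31%
- k = 28: 7×3 + 4×2 = 29; 29/365 = 8%
- k = 35: 0%

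With the stop month also missing, the share is (365 − k)/365, from 98% at k = 8 to 90% at k = 35.

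A year-only start is moved to the Session 1 day when the drug began in the same year: (365 − 60)/365 = 84% if begun 60 days before, (365 − 180)/365 = 51% at 180 days, and 0% at 365 days or more. The rule for a missing day matters much less. It moves a drug to the dosing day in 67% of dates if begun 10 days before, 2% at 30 days and 0% at 60 days.

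**Step 3: an AE that began on the Session 2 day, day missing.** There are 365 × 15 = 5,475 schedules.

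- Both sessions in one month, so the start becomes the Session 1 date. Gaps of 21 to 30 days give 113 + 101 + 89 + 77 + 65 + 53 + 41 + 29 + 18 + 7 = 593 (10.8%).
- Session 2 on the 1st, so the AE stays in its window: 12 × 15 = 180 (3.3%).
- Session 1 on one of the last two days of a month and Session 2 in the next month, so the imputed 1st is Session 1 day 1 or 2. The eligible gaps for the two days together are 23, 21 or 17 when the next month has 31, 30 or 28 days: 7×23 + 4×21 + 17 = 262 (4.8%).
- Outside both windows: 5,475 − 593 − 180 − 262 = 4,440 (81.1%).

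Averaged over events beginning on day 0, 1 or 2, 80% fall outside both windows, 13% move to the Session 1 window and 7% stay. The share outside both is 59% at a 21-day gap, 82% at 28 days and 93% at 35 days. With the month also missing, a Session 2-day event goes to the Session 1 window in 93% of schedules.

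**Step 4: started or taken.** Objective 8, protocol 13.1.2 and the closing bullet of SAP 8.8.3 define the group by use on the day. The category list in SAP 8.8.3 defines it by start, and that section's summaries refer back to the list. A programmer has two definitions and no rule for choosing between them.

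**The case against.** **Few records may be affected.** Staff record AEs and drugs at the end of each session, ask again the next morning, and call on days 2 and 7 with two calls between (protocol 7.3.1 to 7.3.3). An AE from the session day with no recorded day is therefore an unlikely record. This stands. Start dates of long-standing drugs, recalled at Screening, are a more natural place for partial dates, but the documents give no rate for either.

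**The SAP allows replacement.** This stands as a recourse, but it is optional and has no criterion, and for a drug it is unclear which direction is conservative.

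**The planned drug presentation already says taken.** This stands in part. The SAP contradicts itself, and it is not settled that starts will be counted. Moreover, a year-only start with a known earlier stop does no harm under the taken reading, because there is no overlap with the session. It does harm under the start-date reading. The stop rules do harm under the taken reading.

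**Few psychiatric drugs should overlap a session.** Protocol 11.1 to 11.3 has them tapered or withheld, with exceptions, so a reader should not infer that many ongoing drugs are lost. However, protocol 9.2.2.2 and 11.2 allow lorazepam or sleep aids for AEs, so a drug begun before Session 2 and still in use is foreseeable.

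**Session 2 and the higher dose.** A reader might infer that risk at the higher dose will be understated. The documents do not support that. Protocol 13.1.2 and SAP 8.8.2 plan no day 0-2 AE table split by session, and an event moved to the Session 1 window stays in the objective 4 total.

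**Conclusion.** The point holds in a limited form. Followed literally, SAP 8.2.1 can give a drug a start after its own stop, extend a tapered drug across the Session 1 day, and remove a Session 2 event from both day 0-2 windows. Objective 8 has two definitions that can give different counts even with complete dates.

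It would go too far to say that objectives 4 and 8 are miscounted. The date faults reach only records missing a day or month. The 81% and 54% are shares of schedules or calendar dates given such a record, under uniform dates; they are not error rates. Nor does every tapered drug move: a start in an earlier year, or a stop in an earlier month with only the day missing, stays before dosing. The 81% also assumes that AEs are placed by start date, since SAP 8.8.2 says only that they occur in the window.

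This should be corrected before database lock. It does not touch the effectiveness analysis.

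**What to change.** In SAP 8.8.3, define the day 0-2 category by overlap of intake: start on or before day 2, and stop on or after day 0 or ongoing. Use that definition in both the category list and the presentation bullet.

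In SAP 8.2.1:

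- never impute a start later than a known stop;
- do not impute a taper stop later than the date on which taper completion was confirmed;
- for drugs already recorded at Screening, impute a start before the first dose;
- for a partial AE date compatible with one or both sessions, use the session date that agrees with the known month and the stop date, and state a tie rule for when both sessions remain possible;
- say which direction counts as conservative for AEs and for drugs, if the replacement clause is kept.

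Report the number of imputed dates beside the day 0-2 tables.

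The cost is two SAP paragraphs and minor programming, with no new data. The session anchor will place some AEs from other days of the month in a day 0-2 window. The existing rule already errs that way for the first dose, and the count of imputed dates shows how much depends on it.

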8.3 Protocol Deviations

A major deviation will be defined as participants enrolled but did not meet eligibility criteria during the course of the study, or any deviations that affect safety or overall data integrity, particularly if it relates to study endpoints. The number of participants in each protocol deviation

category listed below will be summarized by analysis set. Individual participants will appear in a listing.

Possible protocol deviations include the following categories:

- Participant entered study but did not meet criteria
- Participant developed withdrawal criteria but was not withdrawn
- Participant received excluded concomitant treatment
- Protocol procedure not performed per protocol
- Participant received incorrect treatment or incorrect dose
- Protocol procedure performed out of range
- Miscellaneous

8.4 Baseline Values

Baseline values are from Baseline Visits for all measures, except C-SSRS, AUDIT, DUDIT, resting blood pressure (BP), Body Mass Index (BMI). For C-SSRS, the initial screening visit will be conducted with the 'Lifetime' version of the measure. The Independent Rater Screening assessment of 'Since Last Visit' suicidal ideation and behavior will be used as 'Baseline.' For the AUDIT and DUDIT measures and resting BP, BMI, results collected at Screening will be used as the Baseline value.

8.5 Participant Disposition and Dosing Summary

The Safety Set will be included in the summary of participant disposition and accountability summarized overall. The number and percent of participants who completed or discontinued the study will be displayed with reasons for early termination, where the percent is with respect to the total number of participants. The timepoint of doses and total MDMA (mg) administered will be summarized for the Safety Set.

8.6 Demographics and Baseline Characteristics

Participant demographic data and Baseline characteristics will be summarized descriptively. The demographic data and baseline characteristics will be summarized for the Safety Set and overall.

8.7 Effectiveness Analyses

For all primary, secondary, and exploratory endpoints descriptive statistics (n, mean, standard deviation, median, range, or counts and percentages where appropriate) will be provided overall. Longitudinal CAPS-5 Total Severity Score and SDS item scores will be plotted across visits to characterize the onset of treatment effect.

8.7.1 Primary Effectiveness Analyses

The *de jure* estimand of treatment effectiveness will be used to estimate the change in CAPS-5 score from baseline due to MDMA-assisted psychotherapy on PTSD symptom severity in the intended population of patients with PTSD from any cause. The primary estimator of effectiveness will be the mean change in CAPS-5 Total Severity Scores from Baseline to 14 weeks after start of dosing (Visit 14). Least squares means from a restricted maximum likelihood (REML)-based mixed model for repeated measures (MMRM) will be used to estimate the change

in CAPS-5 from baseline to each visit. CAPS-5 data collected after treatment discontinuation will not be included in the *de jure* estimand. Missing data will not be imputed.

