# 2.1 Primary Objective and Primary End Point

The primary objective of this study is to evaluate the effect of MDMA-assisted psychotherapy on PTSD, as measured by the estimand of change in CAPS-5 Total Severity Score from Baseline (Visit 3) to 13 weeks post Baseline (Visit 14).

The primary endpoint is the change in CAPS-5 Total Severity Score from Baseline (Visit 3) to 13 weeks post Baseline (Visit 14).

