# Medical History

- 9. At Screening, meet DSM-5 criteria for current PTSD with a symptom duration of 6 months or longer.
- 10. At Screening, have at least severe PTSD symptoms in the last month based on PCL-5 total score of 46 or greater.
- 11. May have well-controlled hypertension that has been successfully treated with antihypertensive medicines, if they pass additional screening to rule out underlying cardiovascular disease.
- 12. May have asymptomatic Hepatitis C virus (HCV) that has previously undergone evaluation and treatment as needed.
- 13. At Baseline, have a confirmed diagnosis of PTSD per CAPS-5 and at least severe symptoms in the last month constituting a CAPS-5 Total Severity Score of 35 or greater.
- 14. May have alcohol or substance use disorder if participant is not in withdrawal or requiring detox. Participants must have a plan, agreed upon by investigator, therapy team, and Medical Monitor, to reduce use of alcohol or other substances and to manage symptoms without self-medicating. Enrollment will require that, in the judgment of the investigator, therapy team, and Medical Monitor, the plan for decreasing substance use is realistic and has a good chance of succeeding in order to prevent substance use from impacting the safety or efficacy of the investigational treatment.

- 15. May have a history of or current Diabetes Mellitus (Type 2) if additional screening measures rule out underlying cardiovascular disease, if the condition is judged to be stable on effective management, and with approval by the Medical Monitor.
- 16. May have hypothyroidism if taking adequate and stable thyroid replacement medication.
- 17. May have a history of, or current, glaucoma if approval for study participation is received from an ophthalmologist.

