#### 7.2.2 Baseline: CAPS-5 by Independent Rater

At Visit 3, an IR will measure the Baseline CAPS-5 (referred to as Baseline CAPS-5 T1) via tele-assessment as soon as possible after medication tapering, stabilization, and two Preparatory Sessions are complete. This visit will be recorded to video to establish inter-rater reliability. The scores will be sent as soon as possible to the site staff. A CAPS-5 Total Severity Score of at least 35 is required to meet Enrollment Confirmation criteria. The IR will also administer the DSP-I and SDS.

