#### 7.2.3 Baseline: Preparatory Session 3 and Enrollment Confirmation

Prior to Visit 4, the site team will review the results of the IR visit to ensure that the CAPS-5 Total Severity Score is at least 35. Visit 4 should be scheduled within 6 days of the Baseline CAPS-5 assessment but ideally will take place as close to Experimental Session 1 (Visit 5) as possible, but not on the same day.

At Visit 4, the site team will confirm eligibility by reassessing specified eligibility criteria and ensuring that the participant continues to agree to all lifestyle modifications. If the participant continues to be eligible for the study, enrollment will be confirmed (after approval from the Medical Monitor for the initial participants until confidence is established). If any requirements are not met before or during Visit 4, the participant will be considered a Pre-Dosing Early Termination.

For eligible participants at Visit 4, qualified site staff will ensure at least 3 hours are scheduled for the visit and:

- Collect urine sample for pregnancy test from PABP.
- Perform urine drug test.
- Perform alcohol test (UK only).
- Administer Since Last Visit C-SSRS to determine suicidal risk.
- Actively support participant in the completion of Baseline self-reported measures:
  - o PCL-5- ensure assessment is in relation to index trauma
  - o ACE
  - o BDI-II
  - o CPGS
  - o EQ-5D-5L
  - o SCS
  - o SRNU
  - o EAT-26
  - o UFEC and economic productivity

Completion of the measures does not need to be recorded.

- Complete the third 90-minute Preparatory Session (as described in Section 7.2.1 Preparatory Sessions 1 and 2) with the purpose of confirming all enrollment is met and completing final preparation for the first Experimental Session.
- Remind the participants of lifestyle modifications, including fasting and refraining from using psychoactive or non-approved medications, pertinent prior to the Experimental Session per Section 3.3 Lifestyle Modifications.
- Schedule Visit 5.

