#### 7.4.3 Study Termination

Study Termination (Visit 15) will take place 2 (-1/+7) days after the final CAPS-5 assessment (Visit 14). Participants who have withdrawn from treatment but have continued for follow-up will also complete this assessment immediately upon withdrawal.

The site team will:

- Inquire about any possible changes in health. Assess the participant's mental health and the status of any previously recorded AEs. Record AEs as described in Section 10.0 Safety.
- Inquire about concomitant medication use and adherence.
- Administer Since Last Visit C-SSRS.
- Conduct symptom-directed physical examination if clinically indicated.
- Conduct pregnancy test (at Visit 13, 14 or 15, or earlier if early withdrawal).
- Measure weight (used to calculate BMI).
- Measure blood pressure.
- Provide and discuss a study exit plan.
- Actively support participant in completion of Study Termination self-reported measures:
  - o LEC-5
  - o PCL-5, ensure assessment is in relation to index trauma
  - o BDI-II
  - o CPGS
  - o EO-5D-5L
  - o SCS
  - o AUDIT
  - o DUDIT
  - o SRNU
  - o EAT-26

Completion of the measures do not need to be recorded.

After all Study Termination measures and assessments are completed, the participant is considered terminated from the study. The participant can resume normal everyday life. The study team will provide an Exit Plan, which may include a referral for additional medical or therapeutic care, as described in Section 7.4.4 Exit Plan. Eligible participants will be asked whether they are interested in participating in the LTFU extension study.

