7.0 Sample Size and Power Considerations

MP18 is a one-arm interventional study. Thus, no power nor sample size calculations were required.

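### The Visit 3 CAPS-5 is both the entry test (35 or more) and the baseline in a one-arm study, so the primary change includes regression to the mean and cannot be attributed wholly to treatment

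*SAP*

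**What the plan says.** **The entry test.** Protocol 7.2.2 states: "A CAPS-5 Total Severity Score of at least 35 is required to meet Enrollment Confirmation criteria". Inclusion criterion 13 in section 3.1 says the same, and Table 1 directs that Visit 4 is not performed if enrollment is not confirmed.

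**The baseline.** Protocol 2.1 and SAP 3.1 define the primary endpoint as the change in CAPS-5 Total Severity Score from Visit 3 to Visit 14. The entry reading and the baseline reading are therefore the same number.

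**The design.** SAP 7.0: "MP18 is a one-arm interventional study. Thus, no power nor sample size calculations were required". Protocol Table 7 schedules the CAPS-5 at Visits 3, 8 and 14 only. Protocol 7.3.1.1 considers repeating the baseline only if it falls outside its window.

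**The attribution.** SAP 8.7.1 says that the estimand "will be used to estimate the change in CAPS-5 score from baseline due to MDMA-assisted psychotherapy on PTSD symptom severity". SAP 8.7.2 uses the same causal wording for the SDS, and protocol 13.1.1.1 describes the analysis as measuring the effect of the two sessions.

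**The PCL-5.** It is first used as a screen (section 3.1, criterion 10): "At Screening, have at least severe PTSD symptoms in the last month based on PCL-5 total score of 46 or greater". Table 7 then repeats it at Visits 4, 9, 13 and 15. Protocol 7.2.3 (Visit 4) asks for "PCL-5- ensure assessment is in relation to index trauma" and protocol 7.4.3 (Visit 15) for "PCL-5, ensure assessment is in relation to index trauma". Table 4 types it as an eligibility measure only. It is absent from the objectives (protocol 2.4, SAP 3.4), from the SAP measures (4.1 to 4.4) and from the analyses in SAP 8.7. Under SAP 8.0, data outside the planned analyses go to listings and not to tables or graphs.

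**The concern.** A CAPS-5 score varies from one occasion to the next around a person's usual level. People who score above their usual level on the day of Visit 3 tend to pass the cut-off, and people who score below it tend to be turned away. Those who pass will on average score lower at Visit 14 even if their usual level has not moved. A control arm would show the same fall and it would cancel in the comparison. Here there is no control arm and no second pre-dose CAPS-5, so the fall stays in the estimate. Putting baseline into the mixed model would not remove it, because there is no comparator.

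The blinded central raters (protocol 6.1 and 8.4) limit rating bias but do not undo selection on a noisy score. Neither document mentions regression to the mean.

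Two things are at stake. The primary objective is to evaluate effectiveness. The study is also meant to check the assumptions behind the Phase 3 power calculations (SAP 2.0).

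**Working it through.** The plan gives no figure to reproduce: no sample-size calculation, expected change, SD or retest correlation. The cut-off of 35, the maximum of 40 participants (protocol 4.1) and the 10-point yardstick (SAP 8.7.4) come from the documents. The rest is assumed and shown as a range.

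**Assumptions.** Scores of those reaching Visit 3 are normal before selection, with mean m = 35 to 41, SD s = 8 to 12 and correlation r = 0.7 to 0.9 between Visits 3 and 14 without treatment. True severity does not change.

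**1. Mean shift.** With a = (35 − m)/s and L = φ(a)/(1 − Φ(a)), the expected fall is (1 − r) × s × L.

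- m = 38, s = 10, r = 0.8: a = −0.30, L = 0.3814/0.6179 = 0.617; fall = 0.2 × 10 × 0.617 = 1.23 points.
- m = 38, s = 12, r = 0.7: a = −0.25, L = 0.3867/0.5987 = 0.646; fall = 0.3 × 12 × 0.646 = 2.33 points.
- Smallest on the grid (m = 41, s = 8, r = 0.9): 0.1 × 8 × 0.389 = 0.31.
- Largest (m = 35, s = 12, r = 0.7): 0.3 × 12 × 0.798 = 2.87.

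A wider grid (m = 36 to 44, r = 0.6 to 0.9, same SDs) gives 0.2 to 3.6 points.

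**2. Confidence interval.** Simulating trials of 40 gated participants with no true change, the 95% interval for the mean change lies wholly on the improvement side in about 23% of trials in the first case above and about 37% in the second. The nominal figure is 2.5%.

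**3. Ten-point falls.** The ungated rate is 1 − Φ(10/(s√(2(1 − r)))). The gated rate is simulated.

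| Case | Without gate | With gate | Added by gate |
|---|---|---|---|
| m 38, s 10, r 0.8 | 5.7% | 7.7% | 2.0 points |
| m 38, s 12, r 0.7 | 14% | 19% | about 5 points |

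**4. Cohen's d.** In the first case the gate cuts the baseline SD from 10 to 10 × √(1 + aL − L²) = 10 × √(1 − 0.185 − 0.381) = 6.6. The null shift divided by that SD is 1.23/6.6 = 0.19. SAP 8.7.3 plans a pre-post d without saying which SD standardises it.

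**5. What the PCL-5 can resolve.** With an assumed SD of PCL-5 change of 8 to 12, the 95% half-width is 2.02 × 8/√40 = 2.6 to 2.02 × 12/√40 = 3.8 points for 40 participants. For taper subgroups of 20 it is 2.09 × 8/√20 = 3.7 to 2.09 × 12/√20 = 5.6. Simulating the 46 and 35 gates together with no true change gave a Screening-to-Visit 4 fall of 1.1 to 2.3 points among those treated, which is below these half-widths.

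**The case against.** The strongest reply is that the mean change is an observed quantity and is not miscalculated. Only its cause is in doubt, which is the ordinary limit of any uncontrolled study. This one is openly labelled open-label, one-arm and feasibility, and its overall objective is to explore. The shift is about 1 point in the central case against a 10-point yardstick, on assumed inputs. Because candidates have already passed the PCL-5 screen, the CAPS-5 gate is probably milder than a gate on an unselected group. The documents also do not say how an uncontrolled change would enter the Phase 3 calculation.

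Much of this stands. It limits the size of the point and rules out asking for a different design. It does not justify the causal wording in SAP 8.7.1 and 8.7.2.

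A reader might infer that the PCL-5, repeated before and after dosing, would measure the artefact. The documents do not support that:

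- It is a self-report measure on a different scale.
- Its Screening value is itself gated at 46, so Screening to Visit 4 carries its own regression to the mean. That interval also spans the medication taper and two Preparatory Sessions.
- No cut-off is applied to the Visit 4 PCL-5, but it is not free of selection. It is taken only in those who passed Visit 3, 3 to 6 days later. The CAPS-5 and the PCL-5 entry criterion both refer to the last month, so a transient peak could be in both.

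Nor is the PCL-5 barred from every use. A baseline value could appear under SAP 8.6 and post-hoc work is allowed under 8.7.3, but neither is a planned analysis of PCL-5 change.

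**Conclusion.** The point holds as a matter of attribution and modest bias. The mean change, its interval, the pre-post d and, slightly, the 10-point response rate include regression to the mean, and nothing in the plan separates it from treatment effect. The size is 0.3 to 2.9 points over the assumed grid and 1.2 in the central case. It rests entirely on the assumed mean, SD and correlation, and it is probably small beside a large true change.

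Two stronger readings should be resisted. A reader might take the 19% in the less favourable case as false responders created by the gate, but 14% would occur without it. A reader might also conclude that an observed improvement would be mainly artefact, or that the one-arm design is invalid. Neither the documents nor the calculation shows that.

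**What to change.** 1. In SAP 8.7.1 and 8.7.2, replace the causal phrase with *change from baseline following MDMA-assisted psychotherapy*, and align protocol 13.1.1.1.
2. Add to SAP 8.7.1 a sensitivity table of the expected regression-to-the-mean shift over a stated range of SD and correlation.
3. Report the Visit 3 CAPS-5 for everyone assessed, including those below 35, so that the distribution before selection can be seen.
4. Add the PCL-5 to SAP 4.4 and 8.7.3 as a supportive descriptive summary at Screening and Visits 4, 9, 13 and 15. Show Screening-to-Visit 4 change by taper status, and Visit 4-to-Visit 15 change, with confidence intervals, beside the CAPS-5 change. State that it indicates drift only, and give the reasons listed above.

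No new visits or data are needed. The cost is some wording and a little more analysis. The drift estimates will be imprecise with at most 40 participants, and the claim becomes slightly less favourable.
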